Official title of the study:

Implementation of the Individual Danish Emergency Process Triage (I-DEPT)

Statistical analysis plan

Original version: June 14, 2022, Latest revised version: January 24, 2023 Latest upload date/Document date: March 30, 2023

Clinical trials registration: NCT04571021

Principal Investigator (PI) [name]^{1,2}, M.D., D.M.Sc., Co-PI [name].

Chief Statisticians

[name], [name].

Contributors to analysis and interpretation of data

Statisticians, Primary Investigators and Steering Committee

This document contains the statistical analysis plan for the I-DEPT study. The statistical analysis plan has been completed prior to the availability of the outcome data and aims to clarify the analyses.

Short summary

Triage systems have been implemented in most emergency departments (ED) to minimize crowding and treatment delays that can result in adverse patient outcomes. Triage systems with limited room for clinical judgment are used by emergency departments (EDs) worldwide. The Individual Danish Emergency Process Triage (I-DEPT) is a new simplified triage system with a clinical assessment. I-DEPT is designed to simplify risk prediction and to reintroduce clinical judgment as the central part of triage. In this trial we compare I-DEPT with a traditional triage model in terms of risk prediction and patient outcomes, with a focus on 30-day mortality. Intervention: I-DEPT is a new triage system constructed from data collected from 12 000 ED patient visits at a large Danish hospital. I-DEPT solely consists of a quick score of vital signs followed by a basic clinical assessment by an ED nurse. The final triage level results from a score calculated after measurement of vital signs corresponding to a triage level of 1-4, that is then adjusted by the ED nurse, who can either up-triage (up to 2 steps) or down-triage (1 step) according to clinical assessment with no specific explanation needed. The development of the I-DEPT (former called Copenhagen Triage Algorithm, CTA) has previously been described in detail (1). I-DEPT has previously been compared to the Danish Emergency Process Triage (DEPT) which is a local adaption of Adaptive Process Triage. The two triage systems were compared in a noninferiority, two-center cluster-randomized crossover study, where I-DEPT was non-inferior to a traditional triage algorithm by short term mortality, and superior in predicting 30-day mortality (2).

Control: DEPT; is a local adaption of the Adaptive Process Triage (ADAPT), triage model developed in Sweden in 2006 like most other well-known triage models, was the standard triage model used in the study. It includes the presenting (or chief) complaint in addition to a list of vital signs with cut-off values corresponding to each triage level. These are both registered, and the final triage level is determined by the most urgent triage level assigned Both triage systems identify five levels of urgency with colors (red, orange, yellow, green, and blue). The least urgent of these (the fifth level) was excluded from this study as it is defined as non-emergent patients (e.g. minor injuries) and includes no indication for measuring vital signs.

Aim of the study

The aim of the study is to investigate the impact of I-DEPT that has a systematic involvement of clinical assessment and the possibility to adjust the triage. I-DEPT will be compared to the existing DEPT with a focus on mortality, critical illness/distribution within risk groups and time to assessment

Hypothesis

The main hypothesis is that I-DEPT will be non-inferior to the existing DEPT regarding 30-day mortality.

Timeline

The study will start at October 1, 2020. Due to implementation patients will be enrolled from November 1, 2020 with planned end of inclusion, April 1, 2022. Follow-up will be concluded on May 1, 2022. The primary analysis will be conducted when the last patient has been followed for 30 days and data is available, which is expected to be November 2022.

Study design;

Hospital	1. sep-20	1. okt-20	1. dec-20	1. feb-21	6. april-21	1. juni-21	1. aug-21	1. okt-21	1. dec-21	1. feb-22	1. april-22
Nykøbing Falster Sygehus											
Herlev & Gentofte Hospital											
Sjællands Universitetshospital											
Bispebjerg & Frederiksberg Hospital											
Nordsjællands Hospital											
Slagelse Sygehus, Bomholms Hospital											
Hvidovre & Amager & Glostrup Hospital											
Holbæk Sygehus											
	Baseline										Follow-up
Censureringsperiode											
Studieperiode											
Follow-up periode, 30 dage											

Figure 1: Cluster-randomised step-wedged" design

Note: There was a break between implementation at Bispebjerg og Nordsjaelland

The reason for the break was organisational challenges due to summer holidays with lower staffing in that period.

Inclusion/Exclusion criteria

Eligible Emergency departments

- 1. Located in the Capital Region or Region Zealand in Denmark
- 2. Arrival of acutely admitted patients at the on-site Emergency department
- 3. Systemised use of Triage

Patient inclusion criteria

1. ≥18 years at contact to participating emergency department

Patients will be included at the first admission in the study period (index admission) and will remain in this group (intervention/control) for a follow-up period of 30 days.

All subsequent admissions (readmissions) will be ignored with regards to treatment group (i.e., you stay in the group you were first admitted into).

Exclusion

- Patients presenting in the ED with minor injuries (e.g. sprained ankle or minor cuts/abrasions) as they are triaged as blue (level 5) in both systems which typically precludes measurement of vital signs
- 2. Patient admitted directly to specialty ward (without contact to the emergency department)

Definition of clusters

Eligible hospitals can consist of one or two units. A hospital is defined based on its administrative organisation and catchment area. Each hospital will generate one cluster and two (time) periods (control and intervention). See schematic figure 1

Randomisation

Prior to the study start participating clusters will be randomised to start as either intervention or control. Eight clusters are available. The randomisation were performed using computer-generated numbers.

Ethics

The study was presented to the Regional Ethics Committee, who decided that no formal approval was needed in accordance with Danish law. Data management has been approved by the Danish Data Protection Agency (ID: P-2022-405).

Data:

The first 30 days after implementation of I-DEPT will be censored to minimize carry over effect. At follow-up (30 days after inclusion of last patient) the following data is collected from the National Patient Registry (NPR) and the electronic patient journal system Sundhedsplatformen:

- Contacts with the hospital system in the trial period.
- Information regarding admissions (date, time and place of admission and discharge, admission disrupted by patient).

- Information on vital signs and triage level
- Diagnoses (follow-up during study period, historical and in relation to index admission).
- Date of death or emigration (only very few cases of emigration are expected).

Outcomes:

Following outcomes are registered at clinicaltrials.gov (NCT04571021) on September 30, 2020

I-DEPT= Intervention

DEPT = Control

Primary outcome:

• All-cause mortality within 30 days following triage in the index admission by noninferiority (I-DEPT vs. DEPT)

Secondary outcomes

- All-cause mortality within 2 days following triage in the index admission (I-DEPT vs. DEPT)
- Distribution of patients within triage categories (I-DEPT vs. DEPT) including all-cause mortality within 30-days
 - There are four categories in both triage algorithms used in this study: (green (least urgent), yellow, orange, and red (most urgent))
- Patients in the orange triage category (I-DEPT vs. DEPT) including all-cause mortality within 30-days
 - Number of patients assigned to the orange category previous study showed a significant decrease in this patient group
- Doctor assessment (I-DEPT vs. DEPT)
 - Time from triage to arrival of a doctor Note* Timestamp for arrival of doctor need to be discussed
- Length of stay (I-DEPT vs. DEPT)
 - The total number of days admitted to a hospital within 30 days
- Time in the Emergency Department (I-DEPT vs. DEPT)

- Time spent in the Emergency department from triage to either admission, transfer or discharge
- Patients left without being seen (I-DEPT vs. DEPT)
 - Number of patients leaving the Emergency Department without being assessed by a doctor
- Number of admissions to ICU (I-DEPT vs. DEPT) within 24 hours

Additional secondary outcomes – added July 2022

- Days alive out of hospital within 30 days after admission (I-DEPT vs. DEPT)
- Analyses of primary and secondary outcomes will be repeated with 60 days of censoring after implementation.

[figure not shown]
Additional Post-hoc analyses – added January 2023

- Doctor assessment (I-DEPT vs. DEPT) Time from triage to arrival of a doctor – Note* Timestamp for arrival of doctor need to be discussed – divided into triage groups.
- Analyses of primary and secondary outcomes will be repeated with 90 days of censoring after implementation.

Statistical plan for main outcome paper

Consort diagram:

Schematic consort diagram - following will be reported

Baseline description of groups:

Table 1

	I-DEPT	DEPT	P value
Triage: Red (most urgent), n (%)			p=X
Female, n (%)			
Age, years,			
Systolic Blood Pressure, mmHg			
Heart rate, pr. min			
Respiratory rate, pr. min			
Arterial oxygen saturation, %			
Temperature, degrees Celsius			
Triage: Orange, n (%)			p=X
Female, n (%)			
Age, years,			
Systolic Blood Pressure, mmHg			
Heart rate, pr. min			
Respiratory rate, pr. min			
Arterial oxygen saturation, %			
Temperature, degrees Celsius			
Triage: Yellow, n (%)			р=Х
Female, n (%)			,
Age, years,			
Systolic Blood Pressure, mmHg			
Heart rate, pr. min			
Respiratory rate, pr. min			
Arterial oxygen saturation, %			
Temperature, degrees Celsius			
Triage: Green (least urgent), n (%)			p=X
Female, n (%)			
Age, years,			
Systolic Blood Pressure, mmHg			
Heart rate, pr. min			
Respiratory rate, pr. min			
Arterial oxygen saturation, %			
Temperature, degrees Celsius			
Missing triage			р=X

Table of summary statistics for patients for each group (intervention or control) will be presented for each triage of the four triage groups with baseline variables shown in Table 1.

Continuous variables will be summarized with mean and standard deviation or interquartile range (based on non-missing sample size).

Categorical variables will be reported as frequency and percentages (based on non-missing sample size) and number of missing values.

Categorical variables will be tested with chi-square.

Primary outcome analysis:

The primary outcomes will be an analysis of all-cause mortality within 30 days.

Patients will be followed as one cohort and data will be analysed as randomised and in accordance with the intention-to-treat principle.

- Patients (18+) will be included at the first admission at the participating hospitals in the study period (index admission) and will remain in this group (intervention/control) for follow-up of 30 days.
- Admission is defined as any contact to an emergency department where a Triage is performed
- Any patient lost to follow-up will be censored at the last time known to be alive.

Censored periods: Each period will start with 30 days of implementation, and the end of the study is followed by an observation period of 30 days. Periods of implementation and observation will be censored in the analyses (patients admitted in these periods will not be included in the analyses).

Main analysis

Logistic regression that accounts for clustering with adjustment for hospital ID, age, and sex, period (e.g., calendar month).

Results will be presented with distribution n (%) and Odds Ratio with a 95% Confidens interval and Risk difference with 95% Confidens interval. The assumption is that the actual intervention effect is 0. Non-inferiority will be assessed based on the risk difference with a non-inferiority margin (Δ) of 0.5%.

Cumulative incidence plots (1-survival) will be calculated using the Kaplan-Meier method and presented with Hazard Ratio and 95% Confidens interval and adjusted for the same variables as the main analysis.

Additional cox regression censoring for "Do not resuscitate order" will also be performed.

Sensitivity analyses of the primary endpoint:

In addition to the ITT analysis, a per-protocol analysis will be performed. In this analysis, interventional patients with missing or incomplete triage will be excluded.

Subgroup analyses of primary endpoint:

The primary outcomes will be calculated for the following subgroups, including a test for interactions.

Results will be presented with distribution n (%) and Odds Ratio with a 95% Confidens interval and illustrated in a Forrest plot and/or Cumulative incidence plots (1-survival) will be calculated using the Kaplan-Meier method.

Following subgroups are planned:

- Triage groups (green to red)
- Age (\leq 39 years, 40 to 69 years, \geq 70 years)
- Medical specialties
- Surgical specialties

Secondary endpoints:

Patients in the orange triage category (I-DEPT vs. DEPT) – including all-cause mortality within 30days:

Main analysis

Same as primary outcome:

Logistic regression that accounts for clustering with adjustment for hospital ID, age, and sex,

period

Results will be presented with distribution n(%) and Odds Ratio with a 95% Confidens interval

Doctor assessment (I-DEPT vs. DEPT)

Time from triage to arrival of a doctor

Main analysis

Distribution will be investigated with Boxplot

Cox regression following the same adjustment principles as for the primary outcome (age, sex, hospital id, period)

Results will be presented with Hazard ratio with a 95% Confidens interval

Length of stay (I-DEPT vs. DEPT)

- The total number of days admitted to a hospital within 30 days

Main analysis

Distribution will be investigated with Boxplot

Linear regression following the same adjustment principles as for the primary outcome (age, sex, hospital id, period?)

Results will be presented with mean days (SD or Interquarentile range) for both groups and difference in hours with a 95% Confidens interval

Time in the Emergency Department (I-DEPT vs. DEPT)

- Time spent in the Emergency department from triage to either admission, transfer or discharge

Main analysis

Linear regression following the same adjustment principles as for the primary outcome (age, sex, hospital id, period?)

Results will be presented with mean hours (SD eller Interquarentile range) for both groups and difference in hours with a 95% Confidens interval

Patients left Emergency department without being seen (I-DEPT vs. DEPT)

- Number of patients leaving the Emergency Department without being assessed by a doctor

Main analysis

Analysis – Logistic regression that accounts for clustering with adjustment for hospital ID, age, and sex, period??

Results will be presented with distribution n (%) and Odds Ratio with a 95% Confidens interval

Number of admissions to ICU (I-DEPT vs. DEPT) within 24 hours

Main analysis

Analysis - Logistic regression that accounts for clustering with adjustment for hospital ID, age, and sex, period

Results will be presented with distribution n (%) and Odds Ratio with a 95% Confidens interval

Days out of hospital within 30 days after admission (I-DEPT vs. DEPT)

Main analysis

Distribution will be investigated with Boxplot

Linear regression following the same adjustment principles as for the primary outcome (age, sex, hospital id, period?)

Results will be presented with mean days (SD or Interquarentile range) for both groups and difference in hours with a 95% Confidens interval

Handling of missing data:

The primary outcome analysis should be subject to no or little missing data as it is based on Danish register data. Patients lost to follow-up (tourists) will be censored at the last registration. If more than 5% of data is missing on a variable included in planned analyses, multiple imputation will be introduced.

Additional Post-hoc analyses (planned ultimo July 2022)

Analyses of primary and secondary outcomes will be repeated with 60 days of censoring after implementation.

Analyses of primary and secondary outcomes will be repeated with 90 days of censoring after implementation.

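### The SAP says the two triage systems are compared on risk prediction, but no planned analysis compares prediction, and the within-colour mortality odds ratios cannot stand in for it

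*SAP*

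**What the plan says.** The short summary of the SAP sets out the comparison: "In this trial we compare I-DEPT with a traditional triage model in terms of risk prediction and patient outcomes". It also reports that the previous cluster-randomised crossover trial found I-DEPT "superior in predicting 30-day mortality".

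The formal aim is worded differently: "I-DEPT will be compared to the existing DEPT with a focus on mortality, critical illness/distribution within risk groups and time to assessment". The hypothesis concerns only non-inferiority on 30-day mortality.

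Three planned items touch on mortality by colour:

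- Under Secondary outcomes: "Distribution of patients within triage categories (I-DEPT vs. DEPT) including all-cause mortality within 30-days". No analysis paragraph for this item follows under Secondary endpoints.
- Under Secondary endpoints: a logistic model for 30-day death among orange patients, reported as an odds ratio between arms.
- Under Subgroup analyses of primary endpoint: the primary outcome by triage group, green to red, with an interaction test.

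The colour is set differently in each arm. Under I-DEPT the level comes from a vital-sign score and is then adjusted by the nurse, "who can either up-triage (up to 2 steps) or down-triage (1 step) according to clinical assessment". Under DEPT, "the final triage level is determined by the most urgent triage level assigned".

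**The concern.** A comparison on prediction asks how well the final triage level separates patients who die from those who survive. Nothing in the outcome list or the analysis sections measures that. There is no AUC, sensitivity, specificity, calibration or reclassification measure, and no between-arm contrast of one.

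A reader told that prediction is compared will look to the mortality odds ratios by colour. Those ratios set orange patients under I-DEPT against orange patients under DEPT, and each system decides who is orange. The SAP itself notes, under the orange outcome, that the previous study saw significantly fewer patients in that category. A change in who is orange is therefore foreseeable. An odds ratio away from 1 may then reflect only that change. It could be read as harm or benefit from I-DEPT, or as worse or better prediction, when the truth is the reverse.

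**Working it through.** **Inputs.** The SAP gives no AUC, event count or colour split, so there is no stated figure to reproduce. It does assume a true intervention effect of 0, so every example below keeps the total number of patients and deaths the same in both arms and only moves patients between colours. The colour splits and risks are assumptions.

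**Formulas.** Order the colours from green to red, with d deaths and s survivors in each.

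- AUC = Σ d × (survivors in less urgent colours + s/2) ÷ (all deaths × all survivors). Ties count one half.
- Within-colour odds ratio = (d/s under I-DEPT) ÷ (d/s under DEPT).

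**Assumed DEPT arm.** 10,000 patients and 400 deaths (4%). Patients/deaths: green 3500/35, yellow 3500/105, orange 2600/180, red 400/80. The denominator is 400 × 9600 = 3,840,000. The sum is 60,637.5 + 542,062.5 + 1,452,600 + 755,200 = 2,810,500. AUC = 0.732.

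**Case A, accurate down-triage.** 1200 orange patients with 3% risk (36 deaths) move to yellow. Yellow becomes 4700/141 and orange 1400/144.

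- AUC = 2,871,700 ÷ 3,840,000 = 0.748, so discrimination is better.
- Orange odds ratio = (144/1256) ÷ (180/2420) = 1.54 (crude 95% CI 1.23 to 1.94). The other colours stay at 1.00.

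**Case B, uninformative up-triage.** 1500 yellow patients move to orange at random (3% risk, 45 deaths). Yellow becomes 2000/60 and orange 4100/225.

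- AUC = 2,734,000 ÷ 3,840,000 = 0.712, so discrimination is worse.
- Orange odds ratio = (225/3875) ÷ (180/2420) = 0.78 (crude 95% CI 0.64 to 0.96).

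**Case C, up-triage across all colours.** Green 2800/27, yellow 2600/72, orange 3500/190, red 1100/111. The odds ratios, green to red, are 0.96, 0.92, 0.77 and 0.45. All are below 1 although no death is prevented, and the AUC falls to 0.693.

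**Sensitivity to overall mortality.** At 2% and 6%, case A gives orange odds ratios of 1.51 and 1.57 with the AUC up 0.016. Case B gives 0.79 and 0.77 with the AUC down 0.019 to 0.021.

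**A second assumed split.** Per 100,000 patients, green to red: 30, 36, 30 and 4% with mortality 1, 2.5, 5 and 16%. That is 3340 deaths and an AUC of 0.701. Moving 12,000 patients from orange to yellow gives:

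| Risk of those moved | AUC | Orange OR | Yellow OR |
|---|---|---|---|
| 2% | 0.721 | 1.43 | 0.95 |
| 3.5% | 0.703 | 1.21 | 1.10 |
| 5% (random) | 0.684 | 1.00 | 1.26 |

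**Interaction test.** Return to the first split and set an odds ratio of 0.8 in all four colours, so that there is no interaction, with 400 deaths kept in each arm. Depending on which patients shift, this fits an AUC of 0.707, 0.748 or 0.753, against 0.732 under DEPT. The interaction test does not measure discrimination either.

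**The case against.** The strongest reply is that prediction is not an objective of this plan. The phrase stands only in the short summary; the aim, hypothesis and outcome list agree with one another and omit it. The analysis section is also headed as the plan for the main outcome paper. This stands. It limits the point to a mismatch between the stated comparison and the planned analyses.

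Second, a reader might infer that the trial can say nothing about prediction. The documents do not support that. A table of counts and deaths by colour and arm, if reported in full, yields a crude AUC for each arm. It yields no adjusted difference and no interval that respects the clusters.

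Third, the whole mortality gradient often points the right way. In case A it steepens from 1, 3, 6.9 and 20% to 1, 3, 10.3 and 20%; in case B orange drops to 5.5%. This is fair, but rates alone do not settle it. The three interaction examples share the same four rates and differ only in how many patients sit in each colour, yet their AUCs lie on both sides of the DEPT value.

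Fourth, a reader might take the aim to make the nurse's adjustment a separate question, because it concerns the "impact of I-DEPT that has a systematic involvement of clinical assessment and the possibility to adjust the triage". That clause describes the intervention. The SAP does not set the adjustment as its own comparison, and does not say that the level before adjustment is recorded.

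Finally, an AUC is not free of difficulty. Triage level influences care and hence death, and eight clusters support only an approximate interval. Both belong in the text of the added analysis.

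**Conclusion.** The point holds in a limited form. The SAP names risk prediction as something it compares and plans no measure of it. The within-colour odds ratios that a reader would turn to condition on a colour assigned by the system under test. With no effect on any patient, they can run opposite to discrimination: about 1.4 to 1.5 in orange with a better AUC, or about 0.78 with a worse one.

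The direction was the same at 2%, 4% and 6% mortality. The sizes rest on assumed colour splits, and the crude intervals ignore clustering and covariates. The examples show that the odds ratios can mislead, not that they will in this trial. It would also be wrong to infer a flaw in the primary analysis: all-cause 30-day mortality and its 0.5% margin do not depend on colour, and that test is unaffected.

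**What to change.** - Add, as a secondary or exploratory analysis labelled with its date of addition, the AUC of the four-level final triage for 30-day and 2-day mortality in each arm. Report the between-arm difference, adjusted or standardised for hospital, period, age and sex, with a cluster-respecting 95% CI stated to be approximate with eight clusters.
- Label the orange mortality odds ratio and the triage-group subgroup results as descriptive, not as effects of I-DEPT.
- If prediction is not to be analysed, delete the phrase from the short summary. The descriptive label is still needed.
- Optional: within I-DEPT, compare the vital-sign score level with the nurse-adjusted level, and report mortality in down-triaged patients. Both depend on the pre-adjustment level being recorded or derivable.

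The cost is SAP wording, analysis time and one more secondary analysis. The main analysis needs no new data: the SAP already lists "Information on vital signs and triage level" and date of death among the data collected. It also already carries additions dated July 2022 and January 2023, so a dated addition follows its own practice.

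### Exclusion of level 5 (blue) rests on a level assigned after allocation, by rules that differ between the arms, and the visible SAP text does not test whether both arms lose the same patients

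*SAP*

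**What the plan says.** The exclusion appears in two places and is worded differently in each.

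- **SAP, Control paragraph:** by level. "The least urgent of these (the fifth level) was excluded from this study as it is defined as non-emergent patients", with minor injuries given as an example.
- **SAP, Exclusion:** by presentation. Patients with minor injuries are excluded because "they are triaged as blue (level 5) in both systems which typically precludes measurement of vital signs".

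The two systems arrive at a level differently.

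- **DEPT (Control paragraph):** presenting complaint and vital signs are both registered, and "the final triage level is determined by the most urgent triage level assigned". No downward step is described.
- **I-DEPT (Short summary):** the starting point is "a score calculated after measurement of vital signs corresponding to a triage level of 1-4". The patient is then adjusted by a nurse, "who can either up-triage (up to 2 steps) or down-triage (1 step) according to clinical assessment with no specific explanation needed". No floor at green is stated.

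The Control paragraph says that both systems have five colours. The secondary outcomes say that four are used in the study, with green the least urgent. The Data section lists hospital contacts, triage level, diagnoses related to the index admission, and date of death.

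**The concern.** In this stepped-wedge design a patient's arm is set by hospital and date. The colour is recorded afterwards, by the system under test. Excluding on that colour is excluding on a post-allocation variable that the intervention could affect.

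If the two systems send different shares of otherwise similar patients to blue, the arms lose different low-risk patients. Their 30-day mortality then differs although triage has changed nobody's outcome.

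The planned adjustment for hospital, age, sex and period would not fully remove this. A change in selection that begins when each hospital switches coincides with the intervention term. Hospital and calendar-month terms do not absorb it, and age and sex absorb only the part they explain.

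The primary conclusion is a non-inferiority claim on the risk difference with a margin of 0.5 percentage points, so a shift of a few tenths of a point matters.

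**Working it through.** The SAP gives no control mortality, no sample size and no blue share, so there is no stated figure to reproduce. The check has two parts.

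**1. Can the exclusion depend on the arm?**

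- The Control paragraph excludes on the fifth level, which is an output of triage.
- DEPT uses the presenting complaint. The I-DEPT score does not: it uses vital signs and gives 1 to 4, and clinical judgement follows.
- The SAP does not say how an I-DEPT patient comes to be blue, whether by sorting before the score or by adjustment after it.
- Agreement between the systems on who is blue is therefore asserted in the Exclusion section and does not follow from the rules as described.

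**2. How much could a difference matter?**

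Inputs:
- margin 0.5 percentage points (SAP, Main analysis);
- true intervention effect 0 (same place);
- *m*, 30-day mortality in the arm before any loss: **assumed** 4%;
- *q*, mortality in those dropped: **assumed** 0.2%;
- *s*, share of one arm dropped in excess of the other: **assumed** 2%, 5% or 10%.

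Mortality of those who remain is (m − s·q)/(1 − s), so the shift is s(m − q)/(1 − s).

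| s | Calculation (%) | Mortality after loss | Shift (points) | Share of margin |
|---|---|---|---|---|
| 2% | (4 − 0.02×0.2)/0.98 | 4.08% | 0.08 | 16% |
| 5% | (4 − 0.05×0.2)/0.95 | 4.20% | 0.20 | 40% |
| 10% | (4 − 0.10×0.2)/0.90 | 4.42% | 0.42 | 84% |

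The excess loss that would equal the whole margin is s = 0.5/(m − q + 0.5) = 0.5/4.3 = 11.6%.

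Range, with m from 2% to 6% and q from 0% to 1% (all assumed):
- s = 1%: 0.01 to 0.06 points;
- s = 5%: 0.05 to 0.32 points;
- s = 10%: 0.11 to 0.67 points;
- whole margin: s of about 8% (0.5/6.5) to 33% (0.5/1.5).

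**Direction.** The formula applies to whichever arm loses more low-risk patients. If that is I-DEPT, its mortality rises and the shift works against non-inferiority. If it is DEPT, for instance because its complaint-based rule calls some patients blue whom I-DEPT keeps as green, control mortality rises and the shift favours non-inferiority. The SAP does not allow a choice between these.

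If eligibility does not depend on the level assigned, s = 0 and the shift is 0.

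**The case against.** The strongest reply is that blue is settled before either system acts.

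- The Control paragraph says that level 5 carries no indication for vital signs, while an I-DEPT score exists only once they are measured. A scored patient would then already be past the point that defines blue.
- The secondary outcomes name green as the least urgent category used.
- The Exclusion section says outright that these patients are blue in both systems.
- The two wordings refer to each other, so they may be one rule loosely written.
- Index diagnoses are in the data list, so an exclusion by presentation may be workable.

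Much of this stands. A reader might infer that I-DEPT lets a nurse move a patient from green to blue and so out of the trial. The SAP does not say that; it is an inference from the absence of a stated floor, and the points above weigh against it.

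A reader might also infer that the planned tables would hide any shift. That goes too far. Table 1 gives numbers and percentages per colour and arm, and the distribution across categories is a secondary outcome, so a depleted green group could show there. The content of the CONSORT diagram is not in the text at hand and may include exclusions by arm.

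The reply does not close the point. The Exclusion section says that blue typically precludes vital signs, which is not always. Four categories in use is also what remains once a fifth has been removed. That both systems classify minor injuries alike is an empirical claim about two different rules, and the visible text plans no analysis of the primary outcome that would test it.

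**Conclusion.** The point holds in a limited form. As worded in the Control paragraph, the exclusion acts on a level assigned after allocation by rules that differ between the arms, and it is justified by an untested assumption that they agree. The mortality denominators can therefore differ between the arms.

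The documents do not show that they do differ, and they support neither a size nor a direction of bias. The figure of about 0.2 points for a 5% excess loss shows sensitivity and does not estimate bias; it rests wholly on the assumed 4% and 0.2%. Under those inputs even a 10% loss stays inside the margin, although at higher assumed mortality it need not. A check is worthwhile because the margin is small and the contacts, triage levels and deaths it needs are already in the planned extract.

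**What to change.** 1. Reconcile the Control paragraph and the Exclusion section into one exclusion rule that does not depend on the recorded colour, for example an index minor-injury diagnosis. State how it is applied in the data.
2. State whether an I-DEPT adjustment can end in blue and, if so, how such patients are handled in the analysis.
3. Add a sensitivity analysis of the primary 30-day mortality risk difference in all adult ED contacts with a triage, including blue, using the same model. Say how the index contact is chosen once blue contacts count.
4. Report the blue share by hospital and month, before and after each switch.

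**Cost:** revised wording, one extra model and one descriptive table from contacts, triage levels and death dates already listed; a diagnosis-based rule also needs an agreed code list. **Downside:** adding blue contacts dilutes the population with low-risk patients and tends to pull an absolute difference towards zero, which makes a fixed 0.5-point margin easier to meet. It should therefore remain a sensitivity analysis and not replace the primary one.
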